strategies for efficiently using attention, memory, prospective memory, and problem-solving skills. Action-based cognitive remediation builds on the intensive computerized cognitive training by pairing it with opportunities to apply cognitive skills in simulated real-world environments. Tasks are designed so that participants can immediately transfer the cognitive training to a tangible set of behaviors. This environment provides a platform for the therapist and group members to observe cognition in action and to discuss thoughts related to applying cognitive skills. In addition, both of these approaches place emphasis on setting individual goals that can be linked to the cognitive training.

Once every two weeks, an interventionist will meet with a participant individually, rather than in the group setting. These individual sessions will run concurrently with the group training, with one interventionist meeting with a participant individually and the other interventionist conducting the group-based training with the other participants. In the course of the 48-session training protocol, each participant will engage in 19.5 hours of group bridging activities and 4.5 hours of individual assessment and goal setting. The individual sessions will be used to establish and review progress toward goals.

Transcranial Direct Current Stimulation: TDCS will be administered with a StarStim neuromodulator. This device has been approved for use in research with an investigational device exemption due to meeting criteria for non-significant risk. Following the same procedures as were used during our pilot work, the current will be administered at 1 mA via two saline soaked electrode sponges (5 x 7 cm) for 20 minutes. The electrode placement will be based on the 10/20 EEG system. Specifically, the anodal electrode will be placed over F3 (left dorsal lateral prefrontal cortex) and the cathodal electrode will be placed in the contralateral supraorbital position. The neuromodulator can be programmed to offer tDCS or sham stimulation based upon a participant identification number that is programmed into the device. Thus, the device will administer either tDCS or sham stimulation, depending upon condition assignment, and neither the interventionist nor the participants will know the individual's assignment. Participants who are in the sham condition will receive 30 seconds of stimulation at the beginning of the session to mimic the experience of tDCS. This protocol has been found to be effective and is the recommended protocol for blinded tDCS administration (85).

Integration of Cognitive Training and TDCS. Adaptive versions of two integrative working memory tasks, the N-back and complex span tasks, will be trained on during every session. These tasks will be completed at the beginning of each session and will always be the training tasks used concurrent with tDCS or sham stimulation. These tasks were selected for training in conjunction with stimulation because: 1) they require the coordinated use of multiple working memory components, 2) have each been found to produce generalization, and 3) make independent contributions to the prediction of intelligence, suggesting a strong relationship with other higher order cognitive functions (72).

Study Blinds. To maximize the interpretability of any group differences that occur between the tDCS and sham conditions, multiple blinds will be in place. To equalize expectancy effects, patients will be blind to condition assignment. The StarStim neuromodulator will be used with all participants and is capable of offering a sham stimulation experience that is indistinguishable from tDCS. In addition, to minimize demand characteristics and differential provision of treatment, the interventionists who provide cognitive remediation will be blind to participant condition (tDCS vs sham). Furthermore, steps will be taken to blind the psychology technician who conducts the outcome assessments. Participants will be asked not to describe the intervention they are receiving to the psychology technician. In addition, the technician who conducts the outcome assessments will not provide the clinical intervention. The data collected will be coded in such a way that the investigator who conducts the data analysis will be blind to group membership.

Statistical Analysis Plan. T-tests will be conducted to determine whether important baseline variables are matched, such as working memory performance (N-back performance) and age. If any between-group differences emerge on these factors and they are found to relate to the dependent variables in any of the planned comparisons described below, the confounding variable will be added as a covariate of non-interest in the analysis.

Data Reduction: Consistent with recommendations that change in cognitive function be assessed with multiple measures of the construct (19), each working memory component will be assessed with two measures. Composite scores will be created by averaging the two measures of each aspect of working memory. Composite novel N-Back and novel complex span variables will represent performance on procedurally similar working

memory tasks with novel stimuli, composite scores on capacity, interference control, and goal maintenance tasks will reflect near transfer on untrained working memory measures, the MCCB Speed of Processing and Problem Solving and Reasoning composite will reflect far transfer to a related cognitive domain. Transfer to functional capacity and community functioning will be measured with performance on the UPSA-B Total score and the FE-SFS Total score. Impact on symptom severity will be assessed with the BPRS Total score and the BNSS Total score.

Data Analysis Plan for Aims 1 and 2: Cognitive and functional improvements are considered equally important outcomes for interventions targeting cognition (64). The primary measures of cognitive outcome for this study will be the capacity, interference control, and goal maintenance composites. These variables were selected as the primary outcomes, as near transfer must be demonstrated for an intervention to be deemed cognitively enhancing (19). The measure of functional capacity, the UPSA-B Total score, will be the primary functional outcome. This is consistent with the NIMH criterion that improvement on a measure of functional capacity must be demonstrated in addition to cognitive improvement for an intervention to be classified as cognitively enhancing (86). Thus, near transfer and change in functional capacity are the outcomes that have been deemed to be clinically meaningful. Mixed model approaches will be used, as they are well-suited to examining within subject change over time.

Specific Aim 1: Near and Far Transfer of Training. Mixed effect, repeated measure ANOVAs will be completed to test the hypotheses that WMT and tDCS will enhance performance significantly more than WMT and sham on 1) novel versions of trained tasks, 2) untrained working memory measures, 3) measure of related cognitive functions, 4) functional capacity, and 5) community functioning. Symptom severity is predicted to improve significantly more with WMT and tDCS than WMT and sham. Significant Group x Time interactions will allow rejection of the null hypothesis that WMT + tDCS offers no benefit as compared to sham.

Specific Aim 2: Durability of Cognitive and Functional Changes. To examine durability of near and far transfer and symptom change, mixed model repeated measure ANOVAs will be conducted. TDCS-induced cognitive change is expected to endure and post-intervention between group differences maintained.

References

2. Gold JM. Cognitive deficits as treatment targets in schizophrenia. *Schizophr Res*. 2004;72(1):21-8.

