Restoration of Cognitive Function with TDCS and Training in Serious Mental Illness

9/19/2022

NCT03208036

SPECIFIC AIMS

Development of interventions that can effectively target and remediate the cognitive and functional impairment associated with serious mental illness has been aggressively pursued and is a treatment priority. Transcranial direct current stimulation (tDCS) is a safe, non-invasive neuromodulation technique that is capable of stimulating brain activity to facilitate learning. As such, it shows promise as an adjunctive technique that could potentiate the impact of cognitive remediation and enhance cognition and functioning in this patient population.

The primary objective of this study is to evaluate the pairing of two therapeutic techniques, cognitive remediation and tDCS, as a cognitively enhancing intervention. The efficacy of a cognitively enhancing intervention is critically dependent on its capacity to improve performance on untrained tasks assessing the same cognitive domain. In addition, it would be highly desirable if intervention-induced change also generalized a) to improve functioning on cognitive domains beyond those that are trained and b) to improve capacity to perform real-world cognitive demands. To address this objective, this study is designed to address the following questions. Is cognitive remediation paired with tDCS more efficacious than cognitive remediation delivered with sham stimulation? Is intervention-induced cognitive change sustainable?

Specific Aims.

Specific Aim 1: To examine the incremental benefit of pairing tDCS with cognitive remediation, we will enroll outpatients with schizophrenia, schizoaffective disorder, or bipolar I disorder to a double-blind, double-baseline, sham-controlled study. Working memory focused cognitive remediation concurrent with tDCS or sham will be administered for 48 sessions. We will examine efficacy of the intervention with change on:

- a) novel versions of two working memory training tasks;
- b) untrained measures that assess three domains of working memory performance – goal maintenance, capacity, and interference control (near generalization);
- c) related cognitive constructs (far generalization);
- d) functioning, measured in terms of capacity as well as community participation; and
- e) symptom severity, measure in terms of overall symptom severity and severity of negative symptoms.

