Hypothesis 1: We hypothesize that there will be an incremental benefit to augmenting working memory focused cognitive remediation with tDCS. Specifically, we predict that repeated administration of tDCS will produce 1) greater gains on novel versions of training tasks, 2) greater generalization of performance gains to conceptually similar (near transfer) and related cognitive processes (far transfer), 3) greater change in functioning, and 4) a larger reduction in symptom severity than working memory focused cognitive remediation administered with sham.

Specific Aim 2. The durability of intervention-induced changes in working memory, related cognitive domains, functional capacity, community functioning, and symptom severity will be examined in patients 6 weeks after working memory focused cognitive remediation with tDCS or sham. **Hypothesis 2:** We hypothesize that training gains achieved through pairing tDCS with working memory focused cognitive remediation will be maintained over time so that the predicted post-intervention between group difference in performance is sustained at 6 weeks post-intervention.

Achieving the proposed objectives will yield important information about the efficacy and durability of a novel pairing of cognitively enhancing interventions. Findings will inform treatment development with other cognitively compromised patient populations.

BACKGROUND AND SIGNIFICANCE

Despite pharmacological intervention, serious mental illnesses are among the leading causes of disability (1). This section will review the link between cognition and psychosocial functioning, highlight current efforts to address illness related cognitive impairments, and describe the development of cognitively enhancing interventions.

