Transfer of Working Memory Gains to Functional Outcomes. Development of cognitively enhancing interventions is motivated by the goal of reducing disability in schizophrenia. Recently, the results of two studies suggest that targeting working memory can have a measurable impact on functional outcomes (7, 60). Rispaud et al. (7) found that intervention-induced change in working memory and processing speed during a year of cognitive remediation was predictive of change in functioning, while changes in episodic memory and problem solving were unrelated to functional gains. Similarly, Subramaniam et al. (60) found that intervention induced change in working memory was predictive of vocational functioning at a six month follow up. Research suggests that transfer of cognitive gains to functional outcomes is facilitated by strategy training and opportunities to use cognitive skills with everyday activities (61). The addition of strategy training has been found to increase the impact of cognitive training on functional outcomes, $d=.47$ vs $.34$ (10), while action-based techniques that enable practice of cognitive skills in simulated environments has been found to produce significantly greater functional gains than cognitive training alone (62). Presently, the extent to which tDCS-induced cognitive gains can transfer to functional outcomes is unknown.

RESEARCH DESIGN AND METHODS

Participants will be randomized to a double-blind, double-baseline, sham controlled trial of a 48-session working memory focused cognitive remediation intervention paired with tDCS or sham. All participants who complete the 48-session intervention will be asked to return for follow up assessment 6 weeks post-intervention. A double-baseline design is being used to minimize measurement error, as the largest practice effects are observed between the first and second assessment. Given that very little is known about the durability of tDCS-induced change in cognition, the follow-up assessment will allow us to examine stability.

Participation in this study will be in addition to the clinical care that patients are receiving at study entry and will not replace psychiatric or case management services.

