First Episode Social Functioning Scale (FE-SFS)		X	X	X	X
Brief Psychiatric Rating Scale		X	X	X	X
Brief Negative Symptom Scale		X	X	X	X

Cognitive, Functional, and Symptom Assessment. This set of assessment measures will be administered at baseline, post-intervention (4-month assessment), and at the follow up assessment (5.5-month assessment) to evaluate different degrees of skill transfer and cognitive generalization and to monitor symptom severity.

Symptom Assessment. The Brief Psychiatric Rating Scale (BPRS) (69) and the Brief Negative Symptom Scale (BNSS) (105) will be administered to assess symptom severity in the previous week. With training, good reliability can be obtained on the BPRS and the BNSS with median ICCs of .81-.83 and .89-.95 being reported, respectively (70)(105).

Cognitive tasks administered as part of this assessment include: 1) novel versions of training tasks; 2) untrained working memory measures; and 3) measures of related cognitive constructs. As working memory is a multifaceted construct, and it is unknown whether components of this cognitive domain differ in malleability, near transfer measures were selected so that three distinct components of working memory – capacity, interference control, and goal maintenance could be assessed (71).

N-back task. This task measures executive processes in working memory and requires continuous monitoring, updating, and inhibition of irrelevant items to complete (72). This task presents participants with a series of stimuli that appear sequentially at the center of the computer screen for 500 ms with an inter-stimulus interval of 2000 ms. Participants are required to press one of two buttons identifying each stimulus as a target or a non-target, depending on whether it is a match to the stimulus two before it. Targets will occur on one-third of the trials. The task has demonstrated acceptable retest reliability (ICC = .80-.91), small practice effects (-.07 SD's), and little exposure to ceiling or floor effects (73). D prime, a performance indicator that controls for response bias, will be used to measure performance on this task.

Adaptable N-back tasks will be used as training tasks in the clinical trial. Non-adaptable, novel variants of the N-back tasks will be included in the assessment sessions. N-back tasks will be administered to assess transfer

on procedurally similar tasks with novel content.

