MATRICS Consensus Cognitive Battery (MCCB). This battery was developed specifically for clinical trials of cognitively enhancing agents developed for individuals with schizophrenia (80). The battery assesses 7 domains of cognition that have been identified as impaired in schizophrenia. All subtests have good test-retest reliability, ICC = .68-.85, relatively small practice effects $d = .00-.22$ across a 4-week interval, and little exposure to ceiling or floor effects (80). The MCCB assesses processing speed and reasoning. These domains may show improvement as a secondary effect of enhancing working memory, as working memory supports these cognitive processes (73, 74). The average of T-scores in these two domains will be the measures of far transfer.

Functional measures will be administered to assess functional capacity and community functioning.

University of California, San Diego Performance-Based Skills Assessment-Brief (UPSA-B). This measure of adaptive behavior will be used to assess skillfulness with activities of daily living (81). Participants are asked to complete brief role play tasks so that competence can be rated in two areas: finance and communication. The scores in these two domains are summed to obtain a total score. The UPSA has been validated for use with patients with schizophrenia and was found to have excellent inter-rater reliability (ICC = .91) and test-retest reliability across a 2-week interval, $r = .93$ (81). The brief version of this measure has been found to correlate $r = .91$ with the full measure (108).

First-Episode Social Functioning Scale (SFS). This self-report inventory will be used to assess functioning in the community in the prior 3-month period. This scale was developed for and validated with individuals with schizophrenia. Subscales assess independent living skills, interacting with people, social activities, intimacy, friendships, and family relations. Subscales have been found to have good internal consistency ($\alpha = .63-.80$), to be sensitive to change, and without floor or ceiling effects (82). Subscales 1-5 on actual performance subscales will be summed to generate a total score.

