Randomization. Group assignment will utilize a randomized block strategy, which is the preferred method of group assignment for small clinical trials of this nature (83). Accordingly, groups of 2 to 4 volunteers will be stratified into two groups so that patients assigned to each condition are equivalent in baseline N-back scores and age. We predict groups of this size will accumulate over 6-8 weeks of active recruitment. These stratified groups then will be assigned randomly to treatment conditions. The advantages of the randomized block strategy are that it maintains approximately equivalent group sizes throughout the trial, minimizes the confounding effects of initial differences (thereby decreasing reliance on statistical corrections such as ANCOVA), while at the same time preserving the interpretive strengths of unrestricted randomization.

Table 2. Training Session Protocol	
Training Activity	Time (min)
TDCS/Sham Set Up	5
Lesson Planning	5
Cognitive Training	60
TDCS/Sham Equipment Removal	5
Bridging Activities	45
Total	120

Intervention. The working memory focused cognitive remediation intervention will consist of two components: focused cognitive training and bridging activities. Participants will attend 2-3 120-minute training sessions a week. A typical session protocol is presented in Table 2. To be considered a completer, a participant must complete 80% (39 sessions) of treatment. To maximize treatment completion, make-up times will be available each week. In addition, participants will receive payments for completion of treatment sessions. The payment scale increases by \$1 after every 3 training sessions and ranges from \$10 dollars per a session for the first 3 training sessions and \$25 per a session for the last 3 training sessions.

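### At the 6-week follow-up, about 50-54% of the FE-SFS recall window is training time already scored at the post-intervention visit, so a sustained group difference cannot by itself show that community-functioning gains last

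*Combined protocol and SAP*

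**What the plan says.** Under Specific Aim 2, community functioning is one of the outcomes whose durability "will be examined in patients 6 weeks after working memory focused cognitive remediation with tDCS or sham". Hypothesis 2 expects the group difference seen at the end of training to persist at that point. Research Design and Methods sets the visit: "All participants who complete the 48-session intervention will be asked to return for follow up assessment 6 weeks post-intervention".

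Community functioning has one measure. The Data Reduction paragraph assigns it to the FE-SFS total; the UPSA-B, named alongside, measures functional capacity. The assessment section describes the FE-SFS as a self-report inventory "used to assess functioning in the community in the prior 3-month period". Table 1 schedules it at both baselines, post-intervention (4 months) and follow-up (5.5 months). No different reference period is given for any visit.

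On training length: "Working memory focused cognitive remediation concurrent with tDCS or sham will be administered for 48 sessions", and "Participants will attend 2-3 120-minute training sessions a week". A completer may have fewer sessions: "To be considered a completer, a participant must complete 80% (39 sessions) of treatment".

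The Aim 2 analysis paragraph, whose heading covers functional as well as cognitive change, plans mixed-model repeated-measures ANOVAs. It does not mention the recall window.

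**The concern.** A durability test needs a follow-up score that reflects the period after treatment stopped. Here the recall window is longer than the gap between the last two visits. The follow-up score therefore looks back past the end of training, into weeks that already counted towards the post-intervention score. Part of any group difference at follow-up can be the earlier difference reported again.

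The post-intervention score has a related weakness as the reference value: it averages over the last 3 months of training and does not capture the state at its end.

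If the plan is followed as written, a carried-over FE-SFS difference could be reported as lasting community benefit. The follow-up visit exists because little is known about the durability of these effects, so that conclusion deserves protection.

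**Working it through.** The documents give no overlap figure, so there is nothing of their own to reproduce.

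**Inputs**
- Recall window: 3 months (FE-SFS description), taken as 13 weeks, or 12 if a month is read as 4 weeks.
- Gap from end of training to follow-up: 6 weeks (Research Design and Methods), or 5.5 - 4 = 1.5 months (Table 1).
- Training length T: 48/3 = 16 weeks to 48/2 = 24 weeks (Intervention section). The shortest course for a completer is 39/3 = 13 weeks.
- Assumption: the post-intervention visit falls at the last session.

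**Step 1: training share of the follow-up window** = (window - gap)/window
- 13-week window: (13 - 6)/13 = 7/13 = 54%
- Visit labels in months: (3 - 1.5)/3 = 50%
- 12-week window: (12 - 6)/12 = 50%
- If follow-up slips to 7 or 8 weeks after the last session: (13 - 7)/13 = 46%, or (13 - 8)/13 = 38%

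**Step 2: which weeks these are.** With training ending at week T, the post-intervention window runs from T - 13 to T and the follow-up window from T - 7 to T + 6. They share T - 7 to T, which is 7 weeks. Even the shortest completer course is 13 weeks, so those 7 weeks always lie inside training.

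**Step 3: what the follow-up score would show.** This is an illustration. It assumes a 13-week window, equal recall weight for each week, and a benefit of 1 at the end of training that is either wholly lost or wholly kept after the last session.

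*Constant benefit during training.* Post = 1. Follow-up is 7/13 = 0.54 if lost and 1 if kept.

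*Linear build-up over T weeks.*
- Post = (T - 6.5)/T: 9.5/16 = 0.594 and 17.5/24 = 0.729
- Follow-up if lost = (7/13)(T - 3.5)/T: 0.421 and 0.460
- Follow-up if kept = that value plus 6/13: 0.882 and 0.921

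| Time course | Follow-up as share of post, lost | Follow-up as share of post, kept |
|---|---|---|
| Constant | 54% | 100% |
| Linear, T = 24 | 0.460/0.729 = 63% | 0.921/0.729 = 126% |
| Linear, T = 16 | 0.421/0.594 = 71% | 0.882/0.594 = 149% |

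**Step 4: what an exactly sustained difference would mean.** Let k be the share of the end-of-training benefit kept through the 6 weeks, and set the follow-up value equal to the post value.
- Constant: 7/13 + 6k/13 = 1, so k = 1.
- Linear: (7/13)(T - 3.5)/T + 6k/13 = (T - 6.5)/T, so k = 1 - 10/T. This is 0.58 for T = 24 and 0.375 for T = 16.
- Limiting case, benefit arising only in the last 7 weeks: post = 7/13, so 7/13 + 6k/13 = 7/13 and k = 0.

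The same observed result is compatible with full, partial or no maintenance, depending on when the benefit arose. No FE-SFS is scheduled during training, so the data cannot settle which applies.

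**The case against.** The strongest reply is that the follow-up score still carries information. About 46-50% of its window is after training, and within each time course in the table, loss and full maintenance differ about two-fold. Each loss case in the table shows a drop of 29-46%. An exactly sustained difference with nothing kept needs the limiting case in which all benefit arises in the last 7 weeks. This stands. A reader might infer that the FE-SFS can show nothing about durability, or that the planned comparison is invalid; the documents do not support either. A marked rise or fall would mean something. What fails is reading a sustained difference, taken alone, as lasting gain.

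Second, the effect percentages depend on equal recall weighting, which the documents neither state nor exclude. If respondents weight recent weeks more, carry-over shrinks. This also stands: the percentages are illustrations, whereas the overlap of the windows follows from the schedule.

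Third, the Aim 2 analysis sentence names transfer and symptom change, its stated expectation concerns cognitive change, and Hypothesis 2 speaks of performance, whereas the FE-SFS is self-report. That narrows the point without removing it, because the aim itself lists community functioning and the analysis heading includes functional change.

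Fourth, both arms have the same recall window, so the overlap cannot by itself create a between-arm difference. That is correct, and the between-arm comparison at follow-up remains valid as an estimate over mixed time.

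**Conclusion.** The point holds in limited form. About 50-54% of the follow-up FE-SFS window is training time already scored at the post-intervention visit, given a follow-up 6 weeks (or 1.5 months) after the last session. A sustained FE-SFS group difference therefore cannot by itself support a conclusion that community-functioning gains last. The 54%, 63-71%, 100% and 126-149% figures rest further on equal recall weighting and the assumed time courses.

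A reader might also infer that a merely maintained benefit will look like growth. That follows only if the benefit was still building during the 13 weeks before the post-intervention visit; if it was constant by then, the ratio is 100%.

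The reach is one non-primary outcome and one interpretation of it. The primary outcomes (three working-memory composites and the UPSA-B total) are performance-based, as are the other cognitive measures, and the BPRS and BNSS cover the previous week. None of these is affected. The change is worth making because it alters what the trial may conclude, but it does not threaten the main results.

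**What to change.** In the Aim 2 analysis, state that the FE-SFS post-versus-follow-up comparison will not be used as evidence of durability. Report the follow-up FE-SFS between-arm difference as community functioning over late training plus the first 6 weeks after it. Rest durability claims on the cognitive, UPSA-B and symptom measures. This costs SAP wording only and can be done even if the data are already collected.

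Optionally, for visits still to come, add a reference period of the time since the last training session, in both arms, labelled as a modified recall period. Analyse it only as a between-arm comparison at that visit. It should not enter the repeated-measures comparison with the 3-month post-intervention score, because Time would then be confounded with recall period. The cost is one instruction line and a departure from the scale's stated 3-month window at one visit. If it replaces the 3-month form instead of supplementing it, the mixed-time estimate above is lost for those participants.

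### The arms are matched on baseline N-back and age, but the models would usually omit both; pre-specify them, with time interactions, as a cheap efficiency gain

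*Combined protocol and SAP*

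**What the plan says.** All places are in the combined protocol and SAP.

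- **Randomization.** Groups of 2 to 4 volunteers are split in two so that "patients assigned to each condition are equivalent in baseline N-back scores and age", and the halves are then allocated at random. One stated advantage is "decreasing reliance on statistical corrections such as ANCOVA".
- **Statistical Analysis Plan, opening paragraph.** "T-tests will be conducted to determine whether important baseline variables are matched, such as working memory performance" (N-back) and age. Adjustment has two conditions: "If any between-group differences emerge on these factors and they are found to relate to the dependent variables" in a planned comparison. If both are met, "the confounding variable will be added as a covariate of non-interest in the analysis". No significance level, no criterion for the second condition and no covariate-by-time term is given.
- **Data Analysis Plan for Aims 1 and 2.** "Mixed effect, repeated measure ANOVAs will be completed to test the hypotheses", and the efficacy claim rests on Group x Time. No covariate is listed.
- **Data Reduction.** "Composite novel N-Back and novel complex span variables will represent performance on procedurally similar" tasks. This defines an outcome. It does not say which N-back score, or which of the two baseline visits, feeds the matching or the t-test.

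**The concern.** The t-test looks for an imbalance that the allocation is built to prevent, so it will seldom find one. Whether a variable used in the design enters the model then depends on a rare chance event, and could differ from outcome to outcome.

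Two things are at stake, both about efficiency. If matching balances a variable that predicts change, the unadjusted estimate is already more precise than its standard error says, because the variance explained by that variable stays in the error term; the test is then conservative. Separately, with or without matching, the analysis gives up the ordinary precision gain from a prognostic covariate. In addition, depending on how a triggered covariate is fitted, it may not affect the efficacy test at all.

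**Working it through.** **Inputs.** From the documents: groups of 2 to 4, two matching variables, the two-condition rule, and Group x Time as the test. Assumed, because the documents do not give them: N of 40, 60 or 80; t-test level (0.05 unless stated); how closely groups are split (best possible split, or the better of two random splits, called looser); and R2, the share of variance in change explained by N-back and age together. The plan foresees non-completion ("To be considered a completer, a participant must complete 80% (39 sessions) of treatment") but gives no drop-out rate; 30% at random is assumed where drop-out is mentioned. There is no sample size or power figure in the plan to reproduce.

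**Step 1: how often a t-test flags either variable.** For two independent tests at level a with no matching, P(at least one) = 1 - (1 - a)^2:
- a = 0.05: 1 - 0.95^2 = 9.75%
- a = 0.10: 1 - 0.90^2 = 19%
- a = 0.20: 1 - 0.80^2 = 36%

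With matching, by simulation (level 0.05, complete data, N 40 to 80):

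| Group size | Best split | Looser split |
|---|---|---|
| 4 | 0.1-0.2% | 3.2-3.5% |
| 3 | 0.5-0.6% | 4.1-4.8% |
| Mixed 2-4 | 1.2-1.5% | 4.8-5.1% |
| Pairs | 9.7-9.9% | same |

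Pairs allow only one split, so nothing is matched and the unmatched rate returns. With 30% drop-out the figure for groups of 3, 4 or mixed reaches up to 6.6%. At N=60 with mixed groups and best split, the rate is about 4-5% at level 0.10 and 14-16% at 0.20.

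**Step 2: add the second condition.** If it means a correlation with change at p<0.05, a covariate enters in at most 4.3% of trials (groups of 3, 4 or mixed) or 8.2% (pairs), again at level 0.05.

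**Step 3: type I error of the unadjusted test (nominal 5%), groups of 3, 4 or mixed.**
- R2 = 0.10: 3.9-4.6% (best split), 4.5-5.0% (looser)
- R2 = 0.25: 2.9-3.7% (best split), 4.0-4.6% (looser)
- Pairs: about 5%

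**Step 4: power.** Hand check without matching: 80% power at two-sided 0.05 means effect/SE = 1.960 + 0.842 = 2.802. Adjustment multiplies the SE by sqrt(1 - R2).
- R2 = 0.10: 2.802/0.949 = 2.953; 2.953 - 1.960 = 0.993; power 84.0%
- R2 = 0.25: 2.802/0.866 = 3.235; 3.235 - 1.960 = 1.275; power 89.9%

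These gains of 4.0 and 9.9 points are upper bounds, since they ignore the cost of estimating two coefficients. Simulated difference in power, pre-specified adjustment minus the plan's rule, complete data, in points:

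| R2 | One change score, groups of 3, 4 or mixed | One change score, pairs | Three- or four-visit ANOVA (groups of 4, mixed or pairs) |
|---|---|---|---|
| 0 | -0.4 to -1.9 | -0.8 to -2.1 | -0.4 to -1.6 (pairs -1.1 to -2.5) |
| 0.02 | -0.8 to +0.3 | -1.0 to +0.1 | not run |
| 0.10 | +2.1 to +3.4 | +2.5 to +3.2 | +0.9 to +2.8 |
| 0.25 | +7.2 to +8.7 | +8.5 to +8.8 | +4.6 to +8.1 |

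For one change score, break-even R2 is about 0.01-0.04 with complete data and about 0.05-0.08 at N=40 with 30% drop-out. The worst loss found is 3.5 points (N=40, all pairs, 30% drop-out, R2 = 0).

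**Step 5: form of the covariate.** If the score at each visit contains c·x, where x is the person's baseline value, then post minus baseline contains c·x - c·x = 0. A main effect alone therefore cannot move Group x Time with complete data. In one simulated data set the Group x Time estimate was 0.5935 (SE 0.2903) both with and without the main effect, and 0.4749 (SE 0.2514) once covariate x time was added. With missing visits the identity is only approximate.

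**The case against.** **Matching was chosen in place of ANCOVA.** The Randomization section says so, and the choice does protect against confounding. It does not take the variance explained by the matched variables out of the error term, so the efficiency point stands.

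**The variables may not predict change.** This stands. The plan cites a lack of knowledge about who responds to cognitive remediation, and if R2 is near zero the fix costs a little power.

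**A reader might infer that about 90% or more of trials omit the variables on any reading, because of the matching.** The documents do not support that. The 90% figure is 0.95 squared, the rate for two unmatched tests at an assumed 0.05. The second condition also speaks of relating to the dependent variables, which can mean their level rather than change. On that reading, in a check at N=60 with assumed correlations of 0.5 and -0.3, a covariate entered in about 15% of trials (pairs, level 0.10), 29% (pairs, 0.20) and 12% (mixed groups, best split, 0.20).

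**A reader might infer that the safeguard is inert even when it fires.** That holds only if the covariate is fitted without a time interaction. A repeated-measures ANCOVA fitted as a multivariate model gives the covariate its own coefficient at each visit, so the interaction is already there. The plan does not say which is meant.

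**A reader might infer a biased or invalid result.** Allocation is random within matched groups, and the unadjusted test errs, if at all, on the conservative side.

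**Conclusion.** The point holds as a cheap efficiency improvement, not as the correction of an error. At an assumed 0.05 level the two design variables would usually be left out of the model, and at 0.10 still so for mixed groups with close matching; at looser levels or with pairs, omission is less frequent but remains the more common outcome.

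Most of the possible power gain is the ordinary benefit of a prognostic covariate, since pairs gain as much; what is specific to matching is the mild conservatism. The multi-visit figures are closest to the planned ANOVA and are somewhat smaller than those for one change score. Every figure depends on assumed N, R2, test level and splitting rule. The size of the benefit is therefore unknown, while the range of the loss is small.

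**What to change.** - Report the baseline t-tests descriptively, and do not use them to choose covariates.
- In every primary model, pre-specify baseline N-back and age, each with its interaction with time, whatever imbalance is observed. State the interaction explicitly so that the form of the model is not left to the software.
- Name the N-back score and the baseline visit, and use the same score as in the matching.
- Where N-back is itself the outcome (the novel training-task analysis, which is not primary), model post-baseline scores with baseline N-back as a covariate. The power figures above were not computed for that model and should not be carried over to it.

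The cost is SAP wording and a few degrees of freedom. Both variables are known before allocation, so no new data are needed. If neither predicts change, the price is the small power loss shown in the R2 = 0 row.
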